Table 4: Timeline of Research Tasks

Months	Research Task
0-5	Refine manual, develop adherence scale for control condition, Train educators
	and research assistants, IRB submission, approval
4-5	Specify procedures for random assignment; blinding assessors, develop
	databases, refine recruitment procedures with study and facility staff

5-38	Enroll and study 150 cases (75 treatment, 75 control); Follow-up assessments
39-44	Complete follow-up on last cohorts' cases for 6 months
44-48	Analyze, disseminate data

Tempo: In order to study 14 groups of 3-5 couples each (7 treatment, 7 control) per VISN (3 and 5), each VISN will begin recruitment and individual sessions for two groups, one treatment, one control in study month 5, and continue to enroll and initiate treatment for two additional groups, one in each study condition, every 4-5 months until all groups have been completed and followed, in study month 44. This design will in most cases avoid a long wait for participants between randomization and starting treatment. In cases where one treatment condition becomes "filled", in order to avoid long delays and possible attrition before starting treatment, and permit both interventions to be conducted in tandem, we will allow groups with as many as 8 and as few as 3 couples. The protocol also permits an additional "Joining" session to keep early enrolled couples engaged while later-enrolled couples are being assessed and 'joined". In terms of workload, although there will be overlap between groups, the more labor-intensive work of recruiting, consenting and meeting with individual couples will overlap with the less intensive bi-monthly group meetings for the previously-enrolled two groups and will therefore be feasible.

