Intervention Testing Procedures-Randomization and Maintaining Blind: Following informed consent enrollment, couples will be randomized to one of two treatment conditions (75 to each condition) within each VISN: 1) MFG-mTBI-C, or 2) GHE. To maximize adherence to intervention protocol and avoid inadvertent cross-contamination, each of the two educators at each site will conduct only one intervention, either MFG-mTBI-C or GHE. We will take precautions to ensure the RA's performing outcome assessments and other relevant persons are blind to study condition: 1. Subjects will be randomized to treatment condition using Proc Plan in SAS by an independent research staff member from another project who will place treatment assignments in separate envelopes according to the randomization sequence. To avoid recruitment and/or assessment bias, envelopes will be opened by the independent researcher after informed consent procedures in sequence, and assigned participants will be given a new # according to the randomization schedule; 2. The list linking participant code with treatment assignment will be maintained in a locked cabinet by the PI (who will not perform assessments) and by the study biostatistician (who is in a different location); 3. RA's performing assessments will be blind to educator assignment to treatment condition and will additionally be unaware that each educator is delivering only one treatment. 4. To make # 3 plausible, all educators (and other research staff) will participate in the initial training for both treatments. 5. The PIs will convey new assignments to the appropriate educator who will initiate contact to schedule Joining sessions. 6. All educators will deliver both treatments in closed rooms; 7. The rooms will be equipped identically, with a digital tape recorder; 8. The number and length of sessions will be standardized across conditions; 9. Both MFG-mTBI-C and GHE sessions will be recorded for adherence monitoring so that all participants will have identical files; 10. All data pertaining to session material (e.g., treatment notes) will be stored by educators in a locked or password-protected file separate from that used for assessment data; RA's will not have access to the session files. 11. Participants will be trained not to discuss study procedures except with their study educator or the PI, and study staff (educators and RA's) will only discuss study procedures and assignments with the PI or during supervision. 12. Veterans' VA clinicians will be blind to their treatment assignment; 13. Prior to data analysis, the biostatistician will add an electronic field for treatment group to the data base and the data analyst will be trained not to link assignment with ID code. Thus although RA's will be able to link participant names with ID codes needed for labeling and entering data, etc., they will be blind to treatment assignment using the above measures.

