#### **5.2 Recruitment Methods**

Veteran participants (n=150) will be identified in one of two ways. Study staff will work closely with the clinics and programs within the site hospitals (JJP VAMC, VANYHHS, VAMHCS, DCVAMC), such as poly trauma, PTSD and mental health clinics, primary care, caregiver support programs, OEF/OIF/OND services, and other relevant clinics. Potential participants will be identified based on deployment history to Iraq/Afghanistan, a positive DVBIC screen or if they either meet diagnostic criteria for PTSD or have trauma- or CS of at least moderate severity, and cohabitation with a spouse/partner. Clinicians will then discuss study participation with identified study candidates during a routine clinical visit. Clinicians who obtain verbal consent from Veterans during a routine clinical visit may contact research staff by page to effect an in-person introduction if the clinician and the Veteran agree to this method. As an alternate method, for Veterans who agree to be contacted by the study team, the clinician will hand deliver identifying and preferred contact information to approved research staff. Research staff will then attempt to contact the Veteran using his/her preferred phone number. Veterans will also be recruited within the site hospitals via study fliers and study pocket cards posted/distributed around the site hospitals. Veterans who initiate contact do not need clinician approval but study staff will contact the Veteran's provider with his/her consent to ensure participation would not compromise healthcare. In addition, we will conduct community outreach efforts to Vet Centers, local universities and colleges, and local Community Based Outpatient Centers (e.g., White Plains CBOC), which we will visit in-person to present the study and to supply the relevant contacts persons our study fliers/pocket cards to distribute to potential candidates. All referrals made from non-VA settings will have to be enrolled at VA; otherwise, we will not consider them as eligible participants. No referrals will be made via email. All Veterans referred who express interest in the study will be asked for consent to invite their spouse or partner to participate in an information session about the study. The spouses or partners of consenting Veterans will be approached in one of two ways: 1) the Veteran may either describe the study to their spouse/partner with the assistance of the IRB-approved flier (attached as a supplement), or, 2) if the Veteran prefers, an appointment can be made for the research staff to contact the Veteran and his/her spouse/partner at a convenient time during which the staff member will describe the study and determine interest in participation. The pilot study's initial protocol left the full responsibility of describing the study to the caregiver to the Veteran. However, we discovered that using this method Veterans reported difficulty and/or burden due to the cognitive limitations and disabilities associated with mTBI. The Veterans expressed a preference for the research staff to describe the study in a consultation with their spouse partner. Based on this feedback, we amended our IRB protocol in the pilot study to allow study staff to describe the study to the spouse/partner and the Veteran in an information session at the couple's convenience. We therefore propose to provide Veterans with the two

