.5	25%	90/67	0.05	.79
.6	15%	90/76	0.05	.91
.6	20%	90/72	0.05	.89
.6	25%	90/67	0.05	.87
.7	15%	90/76	0.05	.95
.7	20%	90/72	0.05	.94
.7	25%	90/67	0.05	.93

Calculated for rho = .5; Pilot rho = .833Calculated for rho = .5; Pilot rho = .839

t-test, with alpha=0.05, rho=.50 and effect sizes ranging from .5 to .7. Although attrition in the pilot study was relatively low: 10%, we have conservatively calculated power for higher rates of attrition that that observed in our pilot work: 15%, 20% and 25%, at effect sizes lower than the 1.03 effect size observed for both measures. For the Sydney, we have good power to detect an effect of .5 for Occupational activity, assuming a correlation coefficient of .5, lower than the correlation observed in the pilot study of .83 even with 2.5 times the attrition observed in the pilot study. For the CBI we have good power to detect an effect of .5, lower than the correlation observed in the pilot study of .84, even at 20% attrition, and more power at higher effect sizes or lower levels of attrition. In the unlikely scenario that a substantially lower correlation is observed (.3) along with an effect size half that observed, our power falls somewhat short of conventional standards at higher levels (25%) of attrition (i.e., .70 for Sydney and .68, with a higher correlation coefficient, lower attrition or a larger effect size we have good power to detect a medium to large effect size.

We note that a larger sample size and repeated measures at follow-up will tend to increase the correlation coefficients and reduce the variance of the change over time, most likely resulting in an increase in power. The above power calculation is based on a two-sample t-test which is the simplest form of LMM (with random intercept only) and GEE. If the imbalance between groups on key participant characteristics is minimal, as we anticipate in this randomized trial, this calculation is justified. We chose the more robust approach of using the simpler model and powering our study for a worst case scenario (compared to the effect sizes and correlations

observed in our pilot data) to cover the possibility of a more substantial imbalance, rather than basing our calculations on a more sophisticated model involving many assumptions.

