Secondary Outcomes: We calculated power for the Veteran secondary outcomes, AX (anger expression) and Duke (social support) scales for a two-sided, two-sample t-test, using the same assumptions for calculating primary outcomes and the observed correlation coefficients of .90 and .72, respectively for a two sample t-test, with alpha=0.025. Based on these assumptions, we have 94% power to detect an effect of .5 on the AX scale and 81% power to detect an effect of .5 on the Duke scale. Covariates: Due to the high degree of comorbidity in this cohort of Veterans, we have specified a number of variables for potential inclusion as covariates in our analytic models, should randomization result in an imbalance. These include Veteran (and where appropriate caregiver) physical health, substance use, service use (including starting and stopping treatment), level of depressive and post-traumatic stress symptoms, as well as usual sociodemographic (race/ethnicity, gender, age, SES) and military (e.g., number of deployments) variables. As noted above under General Approach, we will employ t-tests or Wilcoxon ranksum for continuous variables, and chi-square or Fisher's exact tests for categorical variables at baseline to identify any imbalance between groups on these variables, and will control for any imbalance by including variables that differentiate groups at conventional levels by including them in our analyses as covariates. However, as discussed, given random assignment of a sample of 180 to one of two treatment groups, we anticipate that few if any variables will differentiate between groups, and that our power analyses are conservative enough to accommodate inclusion of a limited number of covariates if necessary. Potential inclusion of covariates as "control variables" should be distinguished from inclusion of covariates for the purpose of testing exploratory mediating/moderating hypotheses as described under hypotheses 3 and 4 above.

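### Power is tabulated for 90 couples per arm, but the trial randomises 75; at 75, the good-power claims at effect .5 fail for the CBI at 20% attrition and the Sydney at 25%

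*Combined protocol and SAP*

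**What the plan says.** The sample size is consistent wherever the design is described. The Abstract and the Section 5.1 overview give 150 Veterans. Table 4 has "Enroll and study 150 cases (75 treatment, 75 control" as the enrolment task, the randomisation text says "couples will be randomized to one of two treatment conditions (75 to each condition", and Section 5.2 says "Veteran participants (n=150) will be identified in one of two ways".

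The power calculation in Section 5.6 uses another number. Every row of Tables 8 (Sydney) and 9 (CBI) prints 90 per cell, falling to 76, 72 or 67 after 15, 20 or 25% attrition. The covariate paragraph then refers to "given random assignment of a sample of 180 to one of two treatment groups".

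From these tables, at effect .5 and rho .5, the protocol claims good power:
- for the Sydney, "even with 2.5 times the attrition observed in the pilot study" (2.5 × 10% = 25%);
- for the CBI, "even at 20% attrition, and more power at higher effect sizes or lower levels of attrition".

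For rho = .3 it accepts that "our power falls somewhat short of conventional standards at higher levels (25%) of attrition", giving .70 for the Sydney and a second figure of .68. It also states that "our power analyses are conservative enough to accommodate inclusion of a limited number of covariates if necessary".

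**The concern.** The sample-size justification describes a trial of 180 couples, and the trial will randomise 150. No row of either table shows the power of 75 per arm at the attrition printed beside it. The Sydney is the primary Veteran outcome and the CBI the primary caregiver outcome, so both headline comparisons are affected. A funder, ethics board or monitoring board reading Section 5.6 would credit the trial with a safety margin (effect .5, rho .5, 20 to 25% attrition) that the planned sample may not provide.

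**Working it through.** **Inputs.** Two-sided two-sample t-test on change, alpha .05, rho .5, effect defined as (mt − mc)/mc, pilot changes 3.9 (Sydney) and 18.0 (CBI), attrition 15/20/25%, pilot attrition 10% (all Section 5.6); 75 per arm (Section 5.1). The standard deviation of change is not given, so it is handled in two ways below.

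**Analysed n per arm, rounded down**
- From 90: 90 × .85, .80, .75 = 76, 72, 67, as printed.
- From 75: 75 × .85, .80, .75 = 63, 60, 56.

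**Reproducing the tables.** If the treatment-arm change mt is fixed, mt − mc = mt·e/(1 + e), so the standardised difference is d = K·e/(1 + e) with K = mt/SD. One K per table, 1.518 (Table 8) and 1.437 (Table 9), reproduces all 18 stated powers to within about .005 at n = 76/72/67. The implied SDs are 3.9/1.518 ≈ 2.6 and 18/1.437 ≈ 12.5.

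**Changing only n (effect .5).** Method A solves for d in each stated cell from the noncentral t at its printed n, then recomputes at the smaller n. The range reflects rounding of the stated power (±.005). Method B uses the fitted K.

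| Outcome | Attrition | Stated (n) | d | n from 75 | A (range) | B |
|---|---|---|---|---|---|---|
| Sydney | 15% | .87 (76) | .504 | 63 | .801 (.795–.807) | .804 |
| Sydney | 20% | .85 (72) | .503 | 60 | .780 (.774–.786) | .785 |
| Sydney | 25% | .83 (67) | .507 | 56 | .758 (.753–.764) | .756 |
| CBI | 15% | .84 (76) | .482 | 63 | .766 (.760–.772) | .761 |
| CBI | 20% | .81 (72) | .476 | 60 | .735 (.729–.740) | .740 |
| CBI | 25% | .79 (67) | .481 | 56 | .714 (.709–.720) | .710 |

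**A check that needs no SD.** At the pilot's 10% attrition, 75 × .90 = 67.5, so 67 are analysed. That is the n in the tables' own 25% rows, where the printed power is .83 (Sydney) and .79 (CBI).

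**Attrition the trial can absorb.** For .80 power at effect .5, the fit needs 63 analysed per arm for the Sydney (1 − 63/75 = 16.0%) and 70 for the CBI (1 − 70/75 = 6.7%). Method A with rounding gives 62–64 and 68–72. The CBI therefore tolerates roughly 4 to 9% attrition, below the pilot's 10%.

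**Where power holds, at n = 56**
- Effect .6: Sydney .85; CBI .80–.81 (lowest rounding bound .798).
- Effect .7: Sydney .91; CBI .87–.88.
- Effect .5 with SD scaled by √(2(1 − rho)): at rho .6, .84 and .80; at the pilot rho, about .99 or higher for both.

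**Other figures in the section**
- rho = .3, 25% attrition: Sydney .70 becomes about .61–.63. The text does not attribute .68 to an outcome. If it is the CBI, it becomes about .57–.60.
- Secondary outcomes (alpha .025): if .94 and .81 were computed from 90 per arm, which the text does not restate, they become about .89 (AX) and .73 (Duke).

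**The case against.** The mismatch itself is hard to defend; the strongest reply concerns its consequence. The loss is 6 to 8 points at one effect size and one deliberately low correlation. The protocol rests its caution on planning below the pilot effect and pilot correlation, and most of that margin survives at 75 per arm. No estimand, analysis or procedure changes. This limits the finding but does not remove it: the two good-power sentences are specific to effect .5 and rho .5, and they are not met there.

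Several narrower points stand:
- The .80 threshold is an inference. The protocol claims good CBI power at .81 but not at .79, and calls .70 short of convention, so .80 is a fair reading.
- In the covariate paragraph, 180 directly supports the expectation that few variables will be imbalanced. The statement about conservatism needs restating at 150, not necessarily withdrawing.
- The 67-per-arm rows do describe 75 per arm, at 10% attrition instead of 25%.
- Because the SD is not stated, fitting cannot prove which n was used: a smaller SD with 63/60/56 would fit about as well. The evidence for 90 is the printed column and the figure of 180. If the powers were in fact computed at 75, the powers stand, but that column and the 180 are wrong.

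**Conclusion.** The concern holds. Tables 8 and 9 and the covariate paragraph are built on 90 per arm, against 75 per arm in every design section. Taking the printed n at face value and .80 as the threshold, CBI power at 20% attrition is about .74 and Sydney power at 25% about .76, so neither claim is met. At effect .5 the CBI misses .80 in all three attrition scenarios, and narrowly even at pilot attrition (.79 in the protocol's own table). The Sydney reaches about .80 only at 15%. This does not make the trial unviable: at effects of .6 or more, or at correlations near the pilot's, power remains about .80 or better. It must be corrected because the stated justification belongs to a different sample size.

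Two other items in the section need correcting. The effect of 1.03 reported as observed cannot be on the (mt − mc)/mc scale, because the pilot had no control arm. The 94% secondary power is for the AX scale, whereas Section 5.5 and Hypothesis 1 now use the DERS.

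**What to change.** 1. Recompute Tables 8 and 9 and the rho = .3 scenario at 75 per arm (63/60/56 analysed), and change 180 to 150.
2. Restate the CBI claim at 20% attrition, the Sydney claim at 25% and the statement about room for covariates, with the power threshold named.
3. State the SD of change, and express the target as a mean difference. With the treatment-arm change fixed at the pilot value, ratio .5 means 3.9 − 3.9/1.5 = 1.3 Sydney points and 18 − 18/1.5 = 6 CBI points. Fixing the control-arm change instead would give .5 × 3.9 = 1.95 and .5 × 18 = 9, but that reading misses the tables by up to about .03, so 1.3 and 6 appear to be meant. The protocol should say so.
4. Delete the comparison with 1.03.
5. Recompute secondary power at 75 per arm with n and attrition shown. Drop the AX figure, and give DERS power only with an explicit SD and correlation assumption.

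The cost is revised wording, recomputed tables and less favourable stated power. No participants are added and no study procedure changes.

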## 5.7 Withdrawal of Subjects

Participants can refuse to participate in the study initially or can withdraw from the study at any time after giving consent, which will not interfere with treatment if they are a patient. Subjects that withdraw will be asked for permission to contact them to complete assessments remaining in the study. Any participant (whether a Veteran or spouse/partner) found to have violated the

confidentiality of the group or who causes distress to others, e.g., through verbal aggression or repeated and deemed irremediable disruptions to the group activity after clinician intervention, will be excluded from the intervention and from the study.

